**STUDY PROTOCOL 30 AUGUST, 2017**

## **METHODS**

PRE-POST research project with one ARM (group) and 2 evaluations in each of the times in a cross-over randomized fashion.

### **Inclusion and exclusion criteria**

The metabolic syndrome will be defined according to the presence of three of the criteria published by the International Diabetes Federation: waist circumference > 94 cm for men and > 80 for women of Caucasian ethnicity, high blood pressure figures (> 130 mmHg for systolic and > 85 for diastolic), high fasting blood glucose (> 100 mg / dl) or dyslipidemia: (triglycerides > 150 mg / dl, HDL <40 mg / dl) (1). Participants must be in treatment with ARA II hypotensive drugs. All subjects must be physically inactive, at least during the previous year according to the criteria of the American College of Sports Medicine-ACSM (less than 150 min / week of moderate physical activity or less than 75 min / week of vigorous physical activity).

In addition, participants must not have a diagnosis of any endocrine pathology other than carbohydrate intolerance and their hormonal levels (except insulin) must be within clinical normal ranges. Other exclusion criteria will be, recent surgery, cardiovascular disease (especially uncontrolled coronary disease, heart valve disease, heart failure, complex ventricular arrhythmias), diseases with kidney, liver, respiratory or neuromuscular involvement. Participants will be informed verbally and in writing of the risks and benefits regarding participation in the study and will provide their written consent. Participants will be supervised by their family doctors throughout the study.

### **Intervention with physical training**

The training program will consist of 3 weekly sessions of interval aerobic exercise (EIA). EIA will consist of a cycle ergometer workout (or treadmill running) that includes a 10-minute warm-up period at 70% of the peak heart rate (HRpeak) followed by 5 intervals of vigorous exercise of 4 minutes at 90-95% of your HRpeak interspersed with periods of 3 minutes of active recovery at 70% of HRpeak, ending with a 10-minute cooldown, reaching a total of 55 min duration per workout. Considering the effects of the circadian rhythm on the heart rate, the workouts will be carried out at the same time of day and the load will be adjusted daily to provoke the indicated heart rate. Because of the adaptations produced by exercise, the training load must be adjusted to reach similar heart rates over time and thus comply with the principle of overload for physical training.

### **Nutritional control**

[figure not shown]
During the week prior to the start of the interventions, all participants will keep a written record of their morning weight (completely naked) and of all food consumed with their respective weights. Total energy and macronutrient intake will be evaluated through the individual record of each participant using software adapted to the eating habits of Spaniards (CESNID Nutritional Calculation Program V 1.0 - Center d'Ensenyament Superior de Nutrició i Dietètica assigned to the a University of Barcelona). With these data, the usual caloric intake will be established that will be maintained during the 4 months of intervention to avoid biases due to weight loss resulting from a hypocaloric

diet that would confuse the effects of the training program.

### Evaluation procedure

Participants will go to the laboratory in the morning after an overnight fast and with or without their medication depending on the test. In each one the following measurements will be made:

**Figure 1.** Diagram of the measurements of each of the test.

### Description of the variables to be measured

#### **Anthropometric measurements and blood pressure at rest**

Weight and height will be evaluated using a standard scale and a stadiometer that allows measuring with a precision of 0.1 cm and kg respectively (Seca, Vogel & Halke Hamburg, Germany). The body mass index (BMI; in kg / m^2) will be calculated using the subject's height and weight. The waist circumference (in the horizontal plane 2 centimeters below the rib edge (1)) will be measured using a plastic measuring tape with a precision of 0.1 cm.

To measure blood pressure, participants will be seated in a supine position for 15 min. The systolic (SBP) and diastolic (DBP) blood pressure will then be determined with the help of an ambulatory pressure monitor (SunTec Medical, Oscar, USA). The average of the last 2-3 measurements will be used as the value of the SBP and DBP.

#### **Blood pressure during exercise**

During the exercise we will use a specific pressure meter for this situation that not only has a very sensitive microphone in the pressure cuff but is also integrated with the ECG monitoring through three leads (SunTec Medical, Tango, USA). We will use cuffs adjusted to the size of the participant's arm.

**Post-occlusive reactive hyperemia (PORH).**

After 15 minutes of supine rest, participants will have a flush meter placed on the skin of the forearm (MoorLab, UK). This flowmeter is simply an adhesive probe that with laser technology measures the speed at which the red cells pass through the capillary circulation. Once the signal is good, a pressure cuff will be inflated on the arm 10 mmHg above the resting systolic pressure. The cuff will remain inflated for 3 minutes. After this period of circulatory arrest, the pressure cuff will be opened, and the flow rate will be measured for 2 minutes. This is a measure of the ability of the peripheral vasculature to dilate upon a short-lived ischemic stimulus.

**Pulse wave**

Pulse wave velocity will be measured as an indirect measure of arterial stiffness. For this, a tonometer ( ) placed manually in the carotid and femoral arteries will be used after having measured the distance between them and with reference to the xyloid process. It will be measured sequentially, using the R wave of the electrocardiogram as a reference to synchronize the signals. The time interval is measured at the beginning of the same, since these points correspond to the beginning of the ejection where the possibility of reflections is considered null, the delay being due only to the propagation of the wave.

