**STATISTICAL ANALYSIS PLAN (30 AUGUST, 2017)**

### **Experimental design and calculation of the sample size.**

The experimental scheme that we propose for this research project does not use a parallel control, but the control situation is the PRE training test when the participants are oblivious to the exercise adaptations. Therefore, it is an experimental longitudinal scheme with repeated measures in the same participants. This greatly reduces biological variability since each participant will be compared with himself before and after the intervention, which in this case is training.

In each of the 2 visits where data will be collected for the experiment, four evaluations will be carried out following the scheme of isolating or combining our two factors to study: a) medication and b) exercise.

Thus, we will have the following situations:

a) CONTROL (NO MED, NO TRAIN). Participants have not started training and their habitual antihypertensive medication has been withdrawn for 72 h.

b) MEDICATION. Participants have not started training and they are taking their habitual dose of antihypertensive medication.

b) TRAINED. Participants have completed the 4 months of aerobic exercise training and their habitual antihypertensive medication has been withdrawn for 72 h.

d) EXERCISE + MEDICATION. Participants have completed the 4 months of aerobic exercise training and there are taking their habitual antihypertensive medication.

The group will be composed of 40 participants taking into account that the power analysis of a study in which similar exercise programs (3 months of duration) were used in similar subjects indicates that to observe significant effects on the components of the metabolic syndrome, 27 participants were necessary, so we propose to recruit 30 to have a 10% lack of adherence to the exercise or diet program.

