### **Statistical analysis**

To evaluate the differences between the PRE-training and POST-training situation, repeated measures analysis of variance (ANOVA) will be used, in which the factors associated with both medicine withdrawal (MEDIC vs NO-MEDIC) and training (TRAINED vs NO-TRAINED) will be analyzed. Values of  $P < 0.05$  will be considered significant. Results will be presented as means  $\pm$  SD. All statistical analysis will be performed using SPSS software (version 19.0)

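### Pulse wave velocity is read as arterial stiffness without allowing for the blood pressure that the conditions change, and the path length is not fixed at baseline.

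*Protocol*

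**What the plan says.** **Interpretation.** Protocol, Pulse wave: "Pulse wave velocity will be measured as an indirect measure of arterial stiffness". The section attributes the measured delay wholly to travel of the wave and does not mention blood pressure.

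**Path length.** The same section has the tonometer applied at the carotid and femoral sites "after having measured the distance between them and with reference to the xyloid process". It does not say how the distance is measured, or whether one value serves all tests. Of the tests generally, Protocol, Evaluation procedure, says: "In each one the following measurements will be made".

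**Conditions.** SAP, Experimental design and calculation of the sample size, crosses medication with training. The control condition reads: "Participants have not started training and their habitual antihypertensive medication has been withdrawn for 72 h". The medication condition has the usual dose. Both are repeated when "Participants have completed the 4 months of aerobic exercise training".

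**Analysis.** SAP, Statistical analysis, specifies repeated measures ANOVA in which "the factors associated with both medicine withdrawal (MEDIC vs NO-MEDIC) and training (TRAINED vs NO-TRAINED) will be analyzed". No covariate is named.

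**Pressure data.** Resting pressure is recorded. Protocol, Anthropometric measurements and blood pressure at rest: "The average of the last 2-3 measurements will be used as the value of the SBP and DBP". Neither document links these values to pulse wave velocity.

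**The concern.** A stiffer wall carries the pulse faster, and so does the same wall under higher pressure. Pulse wave velocity (PWV) therefore reflects wall properties and current pressure together. Here one factor is an antihypertensive drug taken or withdrawn, so pressure is manipulated directly. The other factor, training, may also lower it. Comparing each participant with himself or herself does not remove the problem, because pressure differs within the person across conditions. A significant medication or training effect on PWV could be reported as an effect on stiffness when only pressure had changed.

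The second matter is smaller. PWV is distance divided by transit time, so any change in the recorded distance passes straight into PWV. If the distance is measured anew after training, measurement error enters the PRE-POST difference. If body contour has changed, the recorded path could change while the artery does not.

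**Working it through.** **The plan's own figures.** Neither document gives a PWV value, a pressure difference or a standard deviation for PWV, so there is nothing to reproduce on this point. The sample size concerns another outcome: "to observe significant effects on the components of the metabolic syndrome, 27 participants were necessary". With 10% non-adherence, 27/(1 − 0.10) = 30. The same SAP section also gives 40. Below, 27 and 40 serve only as illustrative numbers of participants analysed.

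**Step 1. Pressure, assumed percentage sensitivity.** Assumptions: PWV 10 m/s; sensitivity k of 0.4% to 0.85% per mmHg; wall unchanged.

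Change in PWV = 10 × (1 − exp(−k × ΔP))

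| Fall in pressure | k = 0.004 | k = 0.0085 |
|---|---|---|
| 5 mmHg | 0.20 m/s | 0.42 m/s |
| 8 mmHg | 0.31 m/s | 0.66 m/s |
| 12 mmHg | 0.47 m/s | 0.97 m/s |

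**Step 2. Cross-check with a different model.** With an exponential pressure-area relation and the Bramwell-Hill equation, PWV at fixed intrinsic stiffness is proportional to the square root of pressure. Assume a starting pressure of 90 mmHg and PWV of 10 m/s:

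- 5 mmHg lower: 10 × (1 − √(85/90)) = 0.28 m/s
- 10 mmHg lower: 10 × (1 − √(80/90)) = 0.57 m/s

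Starting pressures of 85 and 100 mmHg give 0.30 and 0.25 m/s for the 5 mmHg fall. Both models point to a few tenths of a metre per second.

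**Step 3. What that does to a test.** Take a shift b = 0.28 m/s due to pressure alone, a paired contrast, two-sided 0.05 (the SAP does not state sidedness) and a normal approximation, with SE = SD/√n:

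P(significant) = Φ(b/SE − 1.96) + Φ(−b/SE − 1.96)

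| Assumed SD of paired differences | n = 27 | n = 40 |
|---|---|---|
| 0.8 m/s | 44% | 60% |
| 1.0 m/s | 31% | 43% |
| 1.5 m/s | 16% | 22% |

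For example, with SD 1.0 and n = 27, SE = 1/√27 = 0.192 and b/SE = 1.455, so Φ(−0.505) ≈ 0.31; the second term is negligible. These are chances of a significant PWV difference with no change in the wall. They are errors only if the result is read as stiffness, in which case the reference is 5%.

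**Step 4. Path length.** PWV = L/Δt, so at equal transit time the percentage change in PWV equals that in L. No change in L gives no change in PWV. A recorded path shorter by 1 cm on 55 cm gives 1/55 = 1.8% (0.18 m/s at 10 m/s); 2 cm on 45 cm gives 2/45 = 4.4% (0.44 m/s). These shortenings are assumed, and nothing in the documents says whether any occurs. Contour bias would bear on PRE-POST only, because contour should not differ between tests with and without medication at one time point. Separately, two independent distance readings with error SD σ add about 2σ²(PWV/L)² to the variance of a difference. A single reading used throughout adds none of this; its error only rescales that participant's values by a common factor.

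**The case against.** **Repeat measurement is not stated.** A reader might infer that the distance is taped again over the abdomen after training and shrinks with the waist. The documents do not support that. The only tape they describe is for waist circumference. The repeat is inferred from Evaluation procedure and Pulse wave read together, and the first of these leads to Figure 1, which is not in the text available here. Protocol, Nutritional control, holds usual caloric intake for the 4 months to limit weight change. Waist is one of the metabolic syndrome components, but the SAP does not say which component determined the 27. What stands is that no rule fixes the distance at baseline.

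**No expected direction.** A reader might also infer that these errors favour the result the sponsor hopes for. Neither document states a hypothesis or direction for PWV, so that cannot be said. Only the medication factor changes pressure by design; pressure after training is an outcome.

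**Adjustment is contestable.** This is the strongest objection. Pressure is measured after each factor has acted and may mediate its effect on PWV, or itself respond to a change in stiffness. Adjusting for it can remove real effect, and cuff error leaves the adjustment incomplete. It would be too strong to make the adjusted estimate the sole basis for any conclusion. Unadjusted PWV remains valid as the total effect. The objection limits what the adjusted analysis can prove, but the unadjusted comparison still cannot distinguish pressure from wall.

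**Standing of the outcome.** PWV is one of several measures, is not named as primary, and is described only as an indirect measure. That bears on priority rather than on whether the gap exists.

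**Conclusion.** The pressure point holds on the documents' own text: PWV is interpreted as stiffness, pressure is manipulated by one factor and may be altered by the other, and the analysis does not allow for it although resting pressure is collected. Under the planned analysis, a lower PWV cannot be separated from a lower pressure. The illustrative size, about 0.2 to 0.7 m/s for 5 to 8 mmHg at 10 m/s, rests entirely on assumed inputs. The physical dependence on pressure does not rest on those figures.

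The path-length point holds only as an omission. The documents leave open whether one baseline distance is used, and their wording suggests measurement at each test. That would add avoidable error to PRE-POST differences. Bias from a change in contour is possible, but its size, including zero, cannot be determined from the documents. A firm claim that the training effect is inflated by a shrinking path would go beyond them.

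This should be corrected before analysis, as it affects the interpretation of a named measure. Nothing here shows that the unadjusted comparison is invalid as a comparison of PWV.

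**What to change.** 1. **Protocol, Pulse wave.** State that the carotid-femoral distance is measured once per participant, at PRE, and that this value is used in all four tests. Cost: one sentence.

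2. **SAP, Statistical analysis.** Keep unadjusted PWV by medication and training as the total effect. Pre-specify a supplementary mixed model with the same two factors plus same-test mean arterial pressure, derived from resting SBP and DBP by one stated formula, as a time-varying covariate. Report both estimates with confidence intervals. Describe a change as pressure-independent stiffness only if the adjusted result supports it, and note that pressure may be a mediator and that cuff error leaves the adjustment incomplete.

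3. **Timing.** State when the resting pressure is taken relative to the PWV recording, so that the covariate reflects pressure close to that recording.

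The adjusted analysis uses data already planned for collection. Its price is a somewhat more complex model than the planned ANOVA, because a covariate that varies between tests does not fit the conventional form, and a wider interval for the adjusted estimate.

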**Blood chemistry analysis**

After a 15-minute supine position and prior to performing the exercise, 10 ml of venous blood will be drawn for the analysis of metabolic syndrome factors in blood. Thus, plasma glucose, insulin, triglycerides, total cholesterol and HDL-cholesterol will be measured.

**STATISTICAL ANALYSIS PLAN (30 AUGUST, 2017)**

### **Experimental design and calculation of the sample size.**

The experimental scheme that we propose for this research project does not use a parallel control, but the control situation is the PRE training test when the participants are oblivious to the exercise adaptations. Therefore, it is an experimental longitudinal scheme with repeated measures in the same participants. This greatly reduces biological variability since each participant will be compared with himself before and after the intervention, which in this case is training.

In each of the 2 visits where data will be collected for the experiment, four evaluations will be carried out following the scheme of isolating or combining our two factors to study: a) medication and b) exercise.

Thus, we will have the following situations:

a) CONTROL (NO MED, NO TRAIN). Participants have not started training and their habitual antihypertensive medication has been withdrawn for 72 h.

b) MEDICATION. Participants have not started training and they are taking their habitual dose of antihypertensive medication.

b) TRAINED. Participants have completed the 4 months of aerobic exercise training and their habitual antihypertensive medication has been withdrawn for 72 h.

d) EXERCISE + MEDICATION. Participants have completed the 4 months of aerobic exercise training and there are taking their habitual antihypertensive medication.

The group will be composed of 40 participants taking into account that the power analysis of a study in which similar exercise programs (3 months of duration) were used in similar subjects indicates that to observe significant effects on the components of the metabolic syndrome, 27 participants were necessary, so we propose to recruit 30 to have a 10% lack of adherence to the exercise or diet program.

### **Statistical analysis**

To evaluate the differences between the PRE-training and POST-training situation, repeated measures analysis of variance (ANOVA) will be used, in which the factors associated with both medicine withdrawal (MEDIC vs NO-MEDIC) and training (TRAINED vs NO-TRAINED) will be analyzed. Values of  $P < 0.05$  will be considered significant. Results will be presented as means  $\pm$  SD. All statistical analysis will be performed using SPSS software (version 19.0)

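### The planned medication-by-training repeated-measures ANOVA, in its standard form, drops a participant when one of four evaluations is missing; a mixed model would avoid a modest, conditional loss of precision

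*SAP*

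**What the plan says.** The SAP, Statistical analysis, gives the method: "To evaluate the differences between the PRE-training and POST-training situation, repeated measures analysis of variance (ANOVA) will be used". The factors named are "medicine withdrawal (MEDIC vs NO-MEDIC) and training (TRAINED vs NO-TRAINED) will be analyzed". Significance is set at P < 0.05 and the software is SPSS 19.0, with no procedure or option specified. Neither document names a mixed model, imputation, an analysis set or a rule for a missing evaluation.

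The protocol, METHODS, describes a one-arm study with "2 evaluations in each of the times in a cross-over randomized fashion", which makes four evaluations per participant. The SAP, Experimental design and calculation of the sample size, says "In each of the 2 visits where data will be collected for the experiment, four evaluations will be carried out", which read literally would make eight. It then lists four situations in all (off and on medication, before and after training), so four is the reading used here. The two sentences should be reconciled.

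The two off-medication situations require a 72 h withdrawal; the two on-medication situations do not.

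On size, the same SAP section gives a group of 40 and also says "27 participants were necessary, so we propose to recruit 30 to have a 10% lack of adherence to the exercise or diet program".

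**The concern.** A two-by-two within-person ANOVA compares contrasts that each use all four of a participant's values. If one value is absent, the participant leaves the analysis of that outcome and the three values that were collected are not used.

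An isolated miss is possible in this design. Only the off-medication evaluations depend on the 72 h withdrawal, so one of them can be lost while its on-medication partner is obtained. With a single group of 30 or 40, discarding usable evaluations widens the intervals for both the training and the medication effect, for no benefit. What is at stake is precision only.

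**Working it through.** **Inputs from the documents.** Two within-person factors (SAP, Statistical analysis); four situations (SAP, Experimental design); N = 40 or 30 (same section).

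**Inputs assumed.** Miss rate p per evaluation of 1%, 3% or 5%; participant share of total variance 0.5-0.8; participant-by-training and participant-by-medication variances each 0 to 1.0 times the residual. The documents give none of these.

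**The plan's own figure.** 27/(1 - 0.10) = 30, so the stated 30 reproduces. The 40 does not follow from those inputs: (40 - 27)/40 = 32.5% loss would be needed. Results are therefore given for both sizes.

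**Step 1: complete cases.** With independent single misses the complete fraction is (1 - p)^4 = 0.961, 0.885, 0.815. Evaluations made by 40 participants number 160(1 - p). Those made by incomplete participants, and so unused, number 160[(1 - p) - (1 - p)^4].

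| p | Complete of 40 | Complete of 30 | Made (N = 40) | Unused |
|---|---|---|---|---|
| 1% | 38.4 | 28.8 | 158.4 | 4.7 |
| 3% | 35.4 | 26.6 | 155.2 | 13.6 |
| 5% | 32.6 | 24.4 | 152.0 | 21.7 |

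**Step 2: precision.** Let S be the 4x4 covariance of a participant's evaluations and c the effect contrast; for training, c is the mean of the two POST values minus the mean of the two PRE values.
- ANOVA variance = c'Sc / (N x complete fraction).
- All-data variance = c'(N x sum over missing patterns of pattern probability x inverse of S for the observed cells)^-1 c.
- The square root of their ratio gives the excess in standard error (SE).

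| p | Training, single misses | Training, off-medication misses only | Training, both evaluations at a time lost | Medication, both evaluations at a time lost |
|---|---|---|---|---|
| 1% | 1.2-1.7% | about 1% | under 1% | under 1% |
| 3% | 3.6-5.4% | 1.8-2.7% | up to 0.7% | 1.5-2.3% |
| 5% | 6.1-9.1% | 3.0-4.5% | up to 1.1% | 2.6-3.9% |

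Hand check at 5%: the mixed model keeps information worth 36.7-38.8 of 40, against 32.6 complete cases. sqrt(36.7/32.6) = 1.061 and sqrt(38.8/32.6) = 1.091. At 3%: sqrt(38.0/35.4) = 1.036 and sqrt(39.3/35.4) = 1.054.

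**Step 3: does it survive fitting?** Step 2 treats S as known. Fitted REML models (n = 40, 2,600 simulations, participant-by-training variance 0.5 and participant-by-medication variance 0.25 times residual) gave SE ratios of 1.046 at 3% and 1.071 at 5%. False positives for training were 5.4% and 5.2% for the mixed model, and 5.4% and 4.8% for the ANOVA. Simulation error is about sqrt(0.05 x 0.95/2600) = 0.4 points. No fitted result with missing data is available for n = 30 or for other variance settings.

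**Step 4: why a random participant effect alone is unsafe.** Take complete data, residual variance 1, participant-by-training variance v at each time and no participant-by-medication variance. The training contrast has true variance 1 + 2v per participant. A model with only a random participant effect pools all three within-person contrasts and uses (3 + 2v)/3. For v = 0.5 that is 1.333 against 2, so the SE is understated by sqrt(1.333/2) = 0.816 and the effective cut-off is 1.96 x 0.816 = 1.60, or about 11% false positives. Simulation (40,000 runs, n = 40) gave 8.4%, 10.8% and 14.2% for v = 0.25, 0.5 and 1.0, against 4.9-5.1% for the ANOVA. At n = 30 it gave 8.3%, 10.8% and 14.2%.

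**The case against.** The strongest reply is that nothing in the plan is wrong. The ANOVA is a valid, standard analysis of this design, and with complete data the change gains nothing. That stands.

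Second, the benefit depends on a pattern the documents do not describe. If participants instead leave before both POST evaluations, the training comparison, which is the SAP's stated aim, gains almost nothing: with 10% lost this way, 0.1-1.1% in SE (2.6-4.0% for medication). At 1% single misses the gain is only 1-2%. Both points stand, and they limit the claim.

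Third, a mixed model brings specification risks that the ANOVA does not have. That also stands, and is why the random effects and the fallback need to be fixed in advance.

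A reader might infer more than the documents support:
- *That the SAP expects 10% missing data, or that 24.4-26.6 complete cases of 30 leaves the study below its required 27.* The 10% is lack of adherence to exercise or diet, not loss of evaluations, and the 27 comes from another study's power analysis.
- *That the result is biased towards completers.* The SAP does write "Participants have completed the 4 months of aerobic exercise training and their habitual antihypertensive medication has been withdrawn for 72 h", but this may only mark when the evaluation takes place. Who is analysed is a separate question from efficiency.
- *That occlusion-test results will often be missing because the protocol says* "Once the signal is good, a pressure cuff will be inflated on the arm". That tells staff to wait for a usable signal; it does not say the test is skipped.

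**Conclusion.** The point holds as an optional improvement, with medium confidence. As specified, the analysis leaves collected evaluations unused whenever a participant misses one of four. The excess in the training SE is about 1-2%, 4-5% or 6-9% at assumed single-miss rates of 1%, 3% or 5%; about 1%, 2-3% or 3-5% if only off-medication evaluations are missed; and about 1% or less when both evaluations at a time go together (up to about 4% for medication). All of this rests on assumed miss rates and variance shares, and on data missing at random. No power figure is attached, because the plan gives no effect size, SD or within-person correlation.

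**What to change.** In the SAP, Statistical analysis, replace the sentence naming the method with wording to this effect:

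> The main analysis of each outcome will be a linear mixed model fitted by REML to all available evaluations, with fixed effects for medication, training and their interaction, and random effects for participant, participant-by-training and participant-by-medication. A model with a random participant effect alone will not be used. The two-factor repeated-measures ANOVA in participants with all four evaluations will be reported as a sensitivity analysis, and will be the main analysis if the mixed model does not converge.

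With complete data this model normally reproduces the planned ANOVA tests, so little is given up.

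The cost is a few sentences, with no extra visit, participant or measurement. The downsides are a missing-at-random assumption, a variance term that may be estimated at zero with 30-40 participants, and two analyses to report.

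### The order of the on- and off-medication tests appears to be randomised, but the planned ANOVA has no order term, so the medication comparison loses precision if first and second tests differ

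*SAP*

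**What the plan says.** The protocol (METHODS) describes one group with "2 evaluations in each of the times in a cross-over randomized fashion". Its Evaluation procedure has participants attending "with or without their medication depending on the test". The SAP (Experimental design and calculation of the sample size) lists four conditions: off and on medication before training, and off and on medication after it. It names medication and exercise as the two factors under study.

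The SAP's Statistical analysis section plans a repeated-measures ANOVA and describes it as one "in which the factors associated with both medicine withdrawal (MEDIC vs NO-MEDIC) and training (TRAINED vs NO-TRAINED) will be analyzed". Neither document mentions a term for order, period or sequence, says whether the two orders are balanced, or says whether a participant's order is drawn again after training.

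One wording point is separate. The SAP also says "In each of the 2 visits where data will be collected for the experiment, four evaluations will be carried out". The protocol, and the SAP's own list of conditions, give two tests before and two after training, four in all. The layout is 2×2 on either reading, so the miscount affects no standard error.

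**The concern.** Training can only run from PRE to POST, so the one thing left to randomise is which of the two medication states is tested first at each time. The protocol does not say this outright, but no other reading fits the design.

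First and second tests may differ for reasons unrelated to the drug, such as familiarity with the procedures. Randomising order keeps such a shift from biasing the medication comparison on average. It does not remove the shift from the error term. A participant tested off medication first has an on-minus-off difference pushed one way, and a participant tested in the other order has it pushed the other way. Without an order term, that spread counts as unexplained variation between participants. At stake is the precision of the comparison for one of the two study factors, and of the interaction if order is redrawn.

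**Working it through.** **The plan's own figure.** The SAP says "27 participants were necessary" and allows 10% non-adherence: 27/(1 − 0.10) = 30, which reproduces its recruitment target. The same sentence says "The group will be composed of 40 participants", which does not follow from 27 and 10%. That is a separate matter. I use n = 40; percentage losses in SE do not depend on n, and with 30 participants every SE below is multiplied by √(40/30) = 1.15.

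**Inputs.** From the documents: the 2×2 within-person layout, randomised order, n = 40 and α = 0.05 (taken as two-sided). Assumed, because the documents give neither: within-person residual SD σ = 6 mmHg, and a constant second-test shift π of 2, 3 or 5 mmHg.

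**Medication contrast.** This is each person's on-minus-off difference averaged over PRE and POST. Each difference has variance 2σ², so the average has variance (2σ² + 2σ²)/4 = σ². The shift enters each difference as +π or −π.

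- Same order at both times: the average carries ±π, adding π².
- Order redrawn at POST: the average carries +π, 0 or −π with probabilities ¼, ½ and ¼, adding π²/2.

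**Interaction.** The POST-minus-PRE difference of differences has variance 4σ². With the same order the shift cancels. With redrawn order it adds 2π².

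**Training contrast.** Each time has one first and one second test, so a constant shift cancels.

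| π (mmHg) | Medication SE, same order: √((36+π²)/40) | Medication SE, redrawn: √((36+π²/2)/40) | Interaction SE, redrawn: √((144+2π²)/40) |
|---|---|---|---|
| 0 | 0.949 | 0.949 | 1.897 |
| 2 | 1.000 (+5%) | 0.975 (+3%) | 1.949 (+3%) |
| 3 | 1.061 (+12%) | 1.006 (+6%) | 2.012 (+6%) |
| 5 | 1.235 (+30%) | 1.101 (+16%) | 2.202 (+16%) |

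**Sensitivity to σ at π = 3.** For σ = 4, 6, 8 and 10 the medication SE rises by 25%, 12%, 7% and 4% (same order), or 13%, 6%, 3% and 2% (redrawn).

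**Size of the test** (simulation, 20,000 runs per case, σ = 6, nominal 0.05, no true medication effect):

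- Balanced order, no order term, π = 2, 3, 5: 0.037, 0.028, 0.010 (same order); 0.043, 0.038, 0.023 (redrawn).
- Balanced order, with the order term: 0.048 to 0.051, with mean SE 0.94 whatever the shift.
- Simple randomisation, no order term: 0.049 to 0.051. The SE honestly reflects chance imbalance in order, which moves the estimate in the realised sample.

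**Power.** Suppose power for medication is 80% with no shift (also an assumption). With balanced order and π = σ/2 (3 mmHg at σ = 6), simulated power without the order term is 72.7% (same order) or 76.6% (redrawn). With the term it is about 80% in both cases.

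**The case against.** The strongest reply is that the SAP's stated purpose is the PRE-to-POST comparison, which a constant shift leaves alone, and that the planned test is valid or conservative. On that view an order term is an optional refinement. It is true that neither the training result nor the false-positive rate is threatened. But the SAP makes medication a study factor in its own right and tests it at the same threshold, so its precision matters.

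A second objection is that σ = 6 with no variation in medication response flatters the percentages. That is fair. If responses vary between participants with SD 4, the base variance becomes 36 + 16 = 52, and shifts of 2, 3 and 5 mmHg raise the SE by about 4%, 8% and 22% (same order) or 2%, 4% and 11% (redrawn). These lie within the sensitivity range shown, since √52 ≈ 7.2. The 12% and 6% are illustrations, not estimates.

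Third, nothing in the documents suggests that first and second tests differ, and the illustration uses a blood-pressure scale although vascular and blood measures are also planned. This also stands: the gain may be nil for some or all outcomes. The cost in that case is close to nil too.

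Finally, a mixed model is a larger change to the plan than one extra term. It is, but it can keep the ANOVA's error structure, and a simple ANOVA version exists if each participant keeps one order.

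**Conclusion.** The concern holds. The design randomises a factor that the analysis then ignores. The consequence is lost precision for the medication contrast, and for the interaction if order is redrawn at POST. It is not bias on average and not excess false positives. The training main effect and the planned means ± SD are unaffected.

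For a 3 mmHg shift, the increase in the medication SE runs from 4% to 25% (same order) or 2% to 13% (redrawn) as σ goes from 10 down to 4 mmHg. All of this rests on assumed values of σ and π, on a shift that is constant across participants and times, and on reading the randomised element as medication order. The change should be made because it costs almost nothing, but the planned analysis is not invalid without it.

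**What to change.** Pre-specify test order (first or second within each time) as a fixed effect. Suggested text: *linear mixed model with medication, training, their interaction and test order as fixed effects, and random effects for participant, participant-by-medication and participant-by-training*.

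The last two random effects keep the separate error terms of the repeated-measures ANOVA. They matter: if medication responses vary with SD 4, a single pooled within-participant error gives a medication SE of 1.01 when the estimate's true SD is 1.13, whereas a separate participant-by-medication error gives 1.13.

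If each participant keeps one order at PRE and POST, the ANOVA itself can do this: add sequence as a between-subject factor together with its interaction with medication. A sequence main effect alone does not help, because the shift enters the medication contrast through that interaction.

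State whether order is redrawn at POST and whether the two orders are balanced. Separately, correct the SAP's count to two evaluations at each of the two times, four in total.

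**Cost:** one term and about one degree of freedom. If there is no order effect, the medication SE is unchanged with balanced order and about 1% larger with simple randomisation (0.956 against 0.943 in simulation). Allocation, visits and participant numbers stay as they are. The order term does not deal with differential carry-over between the two medication states.
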